10.1.4 Populations for Analyses

Toxicity Analysis: All patients will be evaluable for toxicity from the time of E7 TCR T cell infusion. Toxicity data will be collected for all patients.

Response Analysis - Intention to treat: any subjects who enroll onto the trial and provide consent and who receive at least one cycle of treatment will be included in analyses.

10.2 STATISTICAL ANALYSES

10.2.1 General Approach

The fraction of patients who experience a complete response will be reported along with confidence intervals. Only the first treatment course with E7 TCR T cells will be used for this analysis.

10.2.2 Analysis of the Primary Endpoints

The fraction of patients who experience a complete response will be reported along with 80% and 95% two-sided confidence intervals.

10.2.3 Analysis of the Secondary Endpoint

The safety of the E7 TCR T cells will be monitored and any toxicities identified will be reported by type and grade. All treatment courses with E7 TCR T cells will be considered in this analysis.

10.2.4 Safety Analyses

If two of the first six patients develop any grade 4 event related to E7 TCR T cells or grade 3 events (except lymphocyte count increased) that does not resolve to a grade 2 or less in 48 hours or the fraction of participants with these events is greater than or equal to 33% after the initial 6 patients, then no further patients will be accrued as soon as this has been determined. Accrual may resume after appropriate treatment revision is described in approved amendment. All treatment courses with E7 TCR T cells will be considered in this analysis.

10.2.5 Baseline Descriptive Statistics

Baseline demographic characteristics will be reported.

10.2.6 Planned Interim Analyses

As indicated in the two-stage design, the number of complete responses noted after 12 evaluable patients have been treated will be noted and will be used to determine if enrollment to the second stage of accrual may proceed.

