⁷ All patients will follow-up at 1, 2, and 3 months after cell infusion (+/- 7 days). Patients with no response at the 3-month evaluation will be referred for standard of care therapy. Patients with a partial or complete response at the 3-month evaluation will continue to follow up at 4, 5, and 6 months for safety, response, and research evaluations (+/- 7 days). After the 6-month response assessment patients with partial response will be referred for standard of care therapy and patients with a complete response will continue to have follow-up every 3 months (+/- 30 days) for 2 visits, then every 6 months (+/- 30 days) for 2 visits (2 years of follow up total). ⁸As indicated in section 10.4, all subjects \geq age 18 will be offered the opportunity to complete an NIH advanced directives form. This should be done preferably at baseline but can be done at any time during the study as long as the capacity to do so is retained. The completion of the form is strongly recommended, but is not required.

⁹Subjects or local treating physician will be contacted to collect information annually for five years after the date of cell infusion:1) procedures or treatments for vulvar HSIL, 2) procedures or treatments for cervical, vaginal, or anal intraepithelial neoplasia, 3) occurrence of vulvar, cervical, or anal cancer. This followup can be conducted via telephone.

¹⁰Clinical assay may be performed at these time points by the NCI Flow Cytometry Laboratory in the Laboratory of Pathology.

¹¹If applicable, see section 2.1.2.6.

¹²Except for patients previously treated on protocol 17-C-0116.

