5.1.1 Pre cell infusion evaluations

• The following samples may be drawn for research and sent to the ETIB preclinical core within 4 weeks prior to cell infusion. Send to Pre-Clinical Core lab; Attention [name], [name] contact [contact].

- 6 CPT tubes (8mL each). One CPT tube per time point may be used to collect 4mL of plasma, which may be frozen in 4mL vials. PBMC from the remainder of the CPT tubes may be frozen in aliquots of 10 x 106 cells/vial
- 1 SST tube (8mL) for sera. Serum will be processed in the ETIB Pre-Clinical Core and aliquoted into vials of 0.5-1 mL each.
- 5.1.2 Post cell infusion evaluations
 - The following samples may be drawn for research and sent to the ETIB preclinical core While the patient is inpatient, samples may be drawn on post-treatment day 1, posttreatment day 3, thereafter every Monday/Wednesday/Friday x5 days, and then weekly until discharge. Samples may also be collected at each outpatient follow-up visit. Send to Pre-Clinical Core lab; Attention [name], [name] contact [contact].
 - 6 CPT tubes (8mL each). One CPT tube per time point may be used to collect 4mL of plasma, which will be frozen in 4mL vials. PBMC from the remainder of the CPT tubes may be frozen in aliquots of 10 x 10⁶ cells/vial
 - 1 SST tube (8mL) for sera. Serum will be processed in the ETIB Pre-Clinical Core and aliquoted into vials of 0.5-1 mL each.
- 5.1.3 Optional vulvar Biopsies
 - Biopsies for research purposes will be obtained at baseline (within 8 weeks of starting treatment), 10 to 14 days after treatment, 27 to 34 days after treatment, and at the time the patient comes off-treatment (i.e. attains a complete response, experiences progression, or reaches the 6-month time point without a complete response). This biopsy schedule may be repeated for patients receiving retreatment. Clinically indicated biopsies may be obtained at any time by PI discretion if there is concern for invasive cancer.

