6 DATA COLLECTION AND EVALUATION

6.1 DATA COLLECTION

The PI will be responsible for overseeing entry of data into an in-house password protected electronic system (C3D) and ensuring data accuracy, consistency and timeliness. The principal investigator, associate investigators/research nurses and/or a contracted data manager will assist with the data management efforts. All data obtained during the conduct of the protocol will be kept in secure network drives or in approved alternative sites that comply with NIH security standards. Primary and final analyzed data will have identifiers so that research data can be attributed to an individual human subject participant.

All adverse events, including clinically significant abnormal findings on laboratory evaluations, regardless of severity, will be followed until return to baseline or stabilization of event.

Document AEs from the first study intervention, Study Day 0 through 28 days after removal from the study treatment, or until off-study, or until they initiate a new treatment, whichever comes first. Beyond 28 days after the last intervention, or initiation of new treatment as applicable, only adverse events and serious adverse events that are at least possibly related to E7 TCR T cells will be recorded. Grade 1 adverse events will not be recorded.

An abnormal laboratory value will be recorded in the database as an AE **only** if the laboratory abnormality is characterized by any of the following:

- Results in discontinuation from the study
- Is associated with clinical signs or symptoms
- Requires treatment or any other therapeutic intervention
- Is associated with death or another serious adverse event, including hospitalization.
- Is judged by the Investigator to be of significant clinical impact
- If any abnormal laboratory result is considered clinically significant, the investigator will provide details about the action taken with respect to the test drug and about the patient's outcome.

End of study procedures: Data will be stored according to HHS, FDA regulations and NIH Intramural Records Retention Schedule as applicable.

Loss or destruction of data: Should we become aware that a major breach in our plan to protect subject confidentiality and trial data has occurred, this will be reported expeditiously per requirements in section 7.2.1.

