6.3.3.3 Evaluation of Best Overall Response

The best overall response is the best response recorded from the start of the treatment until disease progression/recurrence (taking as reference for progressive disease the smallest measurements recorded since the treatment started).

For Patients with Measurable Disease (i.e., Target Disease)

	Target Lesions	Non-Target Lesions	New Lesions	Overall Response
--	-------------------	-----------------------	----------------	------------------

CR	CR	No	CR		
CR	Non- CR/Non-PD	No	PR		
CR	Not evaluated	No	PR		
PR	Non- CR/Non- PD/not evaluated	No	PR		
Non- CR/Non- PD	Non- CR/Non- PD/not evaluated	No	Non-CR/Non-PD		
PD	Any	Yes or No	PD		
Any	PD*	Yes or No	PD		
Any	Any	Yes	PD		
 In exceptional circumstances, unequivocal progression in non-target lesions may be accepted as disease progression. Note: Patients with a global deterioration of health status requiring discontinuation of treatment without objective evidence of disease progression at that time should be reported as "symptomatic deterioration." Every effort should be made to document the objective progression even after discontinuation of treatment. 					

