6.3.4 Duration of Response

Duration of overall response: The duration of overall response is measured from the time measurement criteria are met for CR or PR (whichever is first recorded) until the first date that recurrent or progressive disease is objectively documented (taking as reference for progressive disease the smallest measurements recorded since the treatment started).

Duration of overall CR: The duration of overall CR is measured from the time measurement criteria are first met for CR until the first date that progressive disease is objectively documented.

Duration of overall non-CR/non-PD: Non-CR/non-PD disease is measured from the start of the treatment until the criteria for progression are met, taking as reference the smallest measurements recorded since the treatment started, including the baseline measurements.

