10.1.3 Sample Size Determination

This trial will be conducted using a Simon minimax two-stage phase II trial design(25) to rule out an unacceptably low CR rate of 5% (p0=0.05) in favor of an improved complete response rate of 25% (p1=0.25). With alpha=0.10 (probability of accepting a poor treatment=0.10) and beta = 0.20 (probability of rejecting a good treatment=0.20), the first stage will enroll 12 evaluable patients, and if 0 of the 12 have a complete response, then no further patients will be accrued. If 1 or more of the first 12 patients have a complete response, then accrual would continue until a total of 16 evaluable patients have been treated. As it may take up to several months to determine if a patient has experienced a complete response, a temporary pause in the accrual may be necessary to ensure that enrollment to the second stage is warranted. If there are 1-2 patients with a complete response out of 16 patients, this would be an uninterestingly low

complete response rate. If there were 3 or more of 16 (18.75%) who experienced a complete response, this would be sufficiently interesting to warrant further study in later trials. Under the null hypothesis (5% complete response rate), the probability of early termination is 54.0%. In patients that undergo retreatment, only the first response to E7 TCR T cell treatment will be used in the calculation of complete response rate.

Since patients will be screened on this protocol, to allow for patients who enroll but are not evaluable for the primary endpoint, as well as screen failures, up to 200 patients total may be enrolled. It is expected that up to 10-12 treated patients can be enrolled within one year; thus, up to 18 months may be required to accrue 16 evaluable patients. Up to 16 patients may be treated in order to allow for a small number of inevaluable, treated patients.

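### Is the date at which 0 complete responses in 12 patients becomes final for the stage 1 decision left open?

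*Combined protocol and SAP*

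**What the plan says.** The stage 1 rule in section 10.1.3 stops accrual if none of 12 evaluable patients has a complete response. Otherwise accrual goes on to 16, and 3 or more CRs justify further study. Section 10.2.6 repeats the interim look: "the number of complete responses noted after 12 evaluable patients have been treated will be noted". Section 10.1.3 adds that a CR may take some months to establish, so "a temporary pause in the accrual may be necessary to ensure that enrollment to the second stage is warranted".

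Four other places bear on when a patient's response status closes:

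- **Section 3.3, calendar footnote 7.** All patients are seen at months 1, 2 and 3. "Patients with no response at the 3-month evaluation will be referred for standard of care therapy". Visits at months 4, 5 and 6 are for partial or complete responders.
- **Section 5.1.3, optional biopsies.** The last research biopsy is taken when the patient comes off treatment, meaning that she "attains a complete response, experiences progression, or reaches the 6-month time point without a complete response".
- **Section 6.3.3.3.** "The best overall response is the best response recorded from the start of the treatment until disease progression/recurrence".
- **Section 6.3.4.** "Non-CR/non-PD disease is measured from the start of the treatment until the criteria for progression are met".

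Section 6.1 limits routine adverse-event recording to 28 days after study treatment, "or until off-study, or until they initiate a new treatment, whichever comes first". The response sections contain no comparable clause on new treatment.

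**The concern.** Take a patient whose disease is stable at month 3. Footnote 7 seems to close her status at month 3, section 5.1.3 at month 6, and sections 6.3.3.3 and 6.3.4 only at progression. If these were rival rules, the stop for no CR in 12 could come 3 months after the twelfth infusion, 6 months after it, or not at all while one stable patient had not progressed. Read literally, section 10.2.6 speaks of patients treated, so the count could even be taken before patient 12 has been assessed.

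Two things would be at stake. The first is the futility stop: if accrual ran on while the team waited, most or all of the four stage 2 patients would be infused before the decision. The second is the final count: a clearance seen after month 3, perhaps after standard care had begun, could move the result from 2 of 16 to 3 of 16, which is the line between not interesting and worth further study. In an open-label single-arm trial, that choice should not be made with the data in view.

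**Working it through.** **1. The stated design.** Inputs from section 10.1.3: an "unacceptably low CR rate of 5% (p0=0.05"), target rate 25%, alpha 0.10, beta 0.20, stop at 0 of 12, success at 3 or more of 16.

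- Probability of stopping at stage 1 is (1 - p)^12. At 5%: 0.95^12 = 0.5404, the plan's 54.0%. At 25%: 0.75^12 = 0.0317.
- Probability of success is P(3 or more of 16) - P(0 of 12) x P(3 or more of the last 4).
- At 5%: 0.0429 - 0.5404 x 0.0005 = 0.0427, within alpha 0.10.
- At 25%: 0.8029 - 0.0317 x 0.0508 = 0.8013, within beta 0.20.

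These figures need every patient to have a settled CR status. They do not depend on the month in which it settles.

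**2. The passages side by side.**

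| Place | What it governs | Does it set the close of CR status? |
|---|---|---|
| Footnote 7 | Follow-up and response visits | Yes: last monthly response visit at month 3 without a response, month 6 with a partial response |
| Section 5.1.3 | Timing of optional research biopsies | No |
| Footnote 4 | The same off-treatment biopsy | No; it ties the month 6 biopsy to a continuing partial response, in line with footnote 7 |
| Section 6.3.3.3 | Best response among those recorded | Only through the visits at which responses are recorded |
| Section 6.3.4 | Durations | No; duration is not a stated objective or endpoint (sections 1.1 and 10.1) |

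Section 6.3.2 has lesions measured at each response evaluation. The calendar grid places response evaluation only in the follow-up column governed by footnote 7. The annual contact in footnote 9 collects later treatments and cancers and may be made by telephone; it does not measure lesions. So the window in section 6.3.3.3, open on its face, is bounded by the visit schedule.

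**3. Timing of the decision.** At the stated 10-12 patients a year, the interval between infusions is 1.0-1.2 months. Patient 12 follows patient 1 by 11 intervals: 11 x 1.0 = 11.0 to 11 x 1.2 = 13.2 months. With no CR seen:

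- decision when patient 12 closes at month 3: 14.0-16.2 months;
- decision when patient 12 closes at month 6: 17.0-19.2 months.

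Without a pause, patients 13-16 would be infused 1, 2, 3 and 4 months after patient 12 (12 a year) or 1.2, 2.4, 3.6 and 4.8 months after (10 a year). That is three or two of them by month 3 and all four by month 6. This is the situation for which section 10.1.3 provides the pause.

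**4. Accrual time.** On the same clock, patient 16 follows patient 1 by 15 intervals: 15.0-18.0 months, in line with the plan's 18. An assumed 3-month pause gives 18.0-21.0 months; an assumed 6-month pause gives 21.0-24.0.

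**5. Late responses.** Suppose a fraction f of CRs first appears after month 3 in patients without response at month 3, and is never counted. The documents give no value for f. The counted rate is 0.25 x (1 - f).

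| f (assumed) | Counted rate | Power |
|---|---|---|
| 0% | 0.25 | 80.1% |
| 5% | 0.2375 | 76.8% |
| 10% | 0.225 | 73.1% |

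This loss comes from a schedule that ends at month 3, not from unclear wording. Stating month 3 more explicitly would recover none of it.

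**The case for a change.** The strongest case for a change is that the statistical section never adopts the calendar. Neither 10.1.3 nor 10.2.6 refers to footnote 7, and treated is not the same as assessed. Section 5.1.3, on its wording, takes in a stable patient at month 6 and so differs from footnote 4. The authors wrote a new-treatment cut-off for adverse events but not for response. The pause is only possible, not required, and has no stated trigger or length. The remedy would be wording alone.

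Much of that is accurate as description. Sections 5.1.3 and footnote 4 do differ and have to be reconciled, which is for the sponsor, but the difference concerns when an optional biopsy falls and cannot alter a CR count. The missing cut-off at new treatment is a real omission of wording. It would matter only if a clearance after standard care entered the count, which needs a response evaluation that the calendar does not schedule for that patient.

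The conditional wording on the pause is also reasonable: once one CR is documented among the first 12, the stage 1 condition is met and there is nothing to wait for. Section 10.1.3 gives the purpose of the pause, which rules out counting at the twelfth infusion and continuing regardless. That one patient separates 2 of 16 from 3 of 16 is true under any cut-off.

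**Conclusion.** No change to the plan follows. Followed as written, it gives a determinate stage 1 decision: 0 of 12 is final when the last of the 12 has completed her scheduled response evaluations, at month 3 without a response and at month 6 with a partial response. The same reading settles the final count.

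The decision boundaries, the 54.0% probability of stopping at a 5% rate and the 80.1% power at 25% are unaffected. The practical effect is on time: with no CR seen by then, a wait of 3 or 6 months after patient 12, and total accrual of 18.0-21.0 or 21.0-24.0 months against 15.0-18.0 without a pause. The plan's 18 months leaves out the pause, but it is a planning estimate on which no inference rests.

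This conclusion assumes that responses are recorded at the scheduled evaluations and that the pause is used when no CR has been documented after patient 12. Both follow from the plan's own text. What remains is an absent cross-reference and an absent cut-off phrase, which analysts would fill in the same way.

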10.2.7 Sub-Group Analyses

None.

10.2.8 Tabulation of individual Participant Data

None.

10.2.9 Exploratory Analyses

Optionally, the following analyses may be done if appropriate and adequate data exist to perform them:

- To evaluate a novel assay to genotype HPV using a ddPCR-based blood test.
- Test for clearance of HPV infection from vulvar tissues.
- Evaluate the expansion, survival, trafficking, phenotype, and function of E7 TCR cells following infusion.
- Investigate the vulvar HSIL microenvironment including immune cell subsets and costimulatory/inhibitory molecules.
- Assess circulating HPV DNA levels associated with treatment.

Any exploratory evaluations which generate quantitative measures will be done using descriptive statistics including confidence intervals when appropriate. Any statistical tests performed for evaluation of exploratory objectives will be done without formal adjustment for multiple comparisons, but in the context of the number of tests performed.

11 COLLABORATIVE AGREEMENTS

11.1 COOPERATIVE RESEARCH AND DEVELOPMENT AGREEMENT (CRADA)

A CRADA (# 03022) between NCI and Kite Pharma is in place. Kite Pharma will be providing funding for this study.

12 HUMAN SUBJECTS PROTECTIONS

12.1 RATIONALE FOR SUBJECT SELECTION

The patients to be entered in this protocol have vulvar HSIL that is unable to be completely resected to negative margins without causing deformity. As only women develop vulvar HSIL, men will be excluded from the study.

Subjects from all racial/ethnic groups are eligible for this study if they meet the eligibility criteria. To date, there is no information that suggests that differences in drug metabolism or disease response would be expected in one group compared to another. If differences in outcome that correlate to ethnic identity are noted, accrual may be expanded or a follow-up study may be written to investigate those differences more fully.

12.2 STRATEGIES/PROCEDURES FOR RECRUITMENT

Patients for this protocol will be recruited via standard CCR mechanisms. This protocol may be abstracted into a plain language announcement posted on NIH websites and on NIH social media platforms. All advertisements, letters and other recruitment efforts will be submitted to the IRB for approval prior to their implementation.

12.3 PARTICIPATION OF CHILDREN

The efficacy of this treatment is unknown, and no safety data in children exist; children are therefore excluded from participation. In addition, vulvar HSIL is exceedingly rare in children so a small number of children, if any, would be eligible to participate. The protocol has defined risks based on prior studies with E7 TCR T cells.

12.4 PARTICIPATION OF SUBJECTS UNABLE TO GIVE CONSENT

Adults unable to give consent are excluded from enrolling in the protocol. However re-consent may be necessary and there is a possibility, though unlikely, that subjects could become decisionally impaired. For this reason and because there is a prospect of direct benefit from research participation (section 12.6), all subjects \geq age 18 will be offered the opportunity to fill in their wishes for research and care, and assign a substitute decision maker on the "NIH Advance Directive for Health Care and Medical Research Participation" form so that another person can make decisions about their medical care in the event that they become incapacitated or cognitively impaired during the course of the study. Note: The PI or AI will contact the NIH Ability to Consent Assessment Team (ACAT) for evaluation as needed for the following: an independent assessment of whether an individual has the capacity to provide consent; assistance in identifying and assessing an appropriate surrogate when indicated; and/or an assessment of the capacity to appoint a surrogate. For those subjects that become incapacitated and do not have pre-determined substitute decision maker, the procedures described in NIH HRPP SOP 14E for appointing a surrogate decision maker for adult subjects who are (a) decisionally impaired, and (b) who do not have a legal guardian or durable power of attorney, will be followed.

